7.8. Immunogenicity

Immunogenicity data will be listed separately for anti-pegcetacoplan peptide antibody and anti-PEG antibody results. The number and percentage of samples confirmed positive for ADA response will be summarized by treatment groups (i.e., PM, PEOM, and Sham). The number and percentage of subjects with treatment-emergent and treatment-boosted responses will be presented by treatment group. Treatment emergent response is defined as a confirmed positive antibody result postdose after a negative antibody result reported at baseline. Treatment-boosted response is defined as a ≥ 4 -fold increase in titer from the baseline level.

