### **12.8.1. Anti-Therapeutic Antibodies**

Data on anti-therapeutic antibodies directed against pegcetacoplan will be summarized by the number and percentage of subjects with confirmed positive anti-therapeutic antibodies.

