2.2.5. Safety Endpoints

- Incidence and severity of ocular and systemic treatment-emergent adverse events.
- Incidence of ADA directed against pegcetacoplan peptide or PEG.
- Incidence of new active CNV in the study eye.
- Incidence of new onset of subclinical CNV in the study eye.
- Incidence of subjects who lost letters based on NL-BCVA categories (≥ 15 , $\geq 15 - < 30$, ≥ 30 ETDRS letters).
- Change/shift from baseline in clinical labs and incidence of abnormal lab values.
- Change from baseline in vital signs and incidence of abnormal vital sign results.
- Shift from baseline in ocular examination assessments including slit-lamp examination and indirect ophthalmoscopy.
- Change from baseline in Intra Ocular Pressure (IOP) and incidence of IOP above specified thresholds.
- Change/shift from baseline in ocular imaging assessments (including specular microscopy; select sites).

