13. DATA HANDLING CONVENTIONS

13.1. General Data Reporting Conventions

Continuous variables will be summarized using the number of non-missing observations (n), mean, SD, median, quartile 1, quartile 3, minimum, and maximum. Geometric mean and CV will be included for PK parameters, where appropriate. Categorical variables will be summarized using frequencies and percentages. Unless stated otherwise, for all percentages, the number of subjects in the analysis population for the treatment group will be the denominator.

Unless otherwise specified, the estimated mean and median for a set of values should be printed out to 1 more decimal place than the original values, and standard deviations should be printed out to 2 more decimal places than the original values. The minimum and maximum should report the same number of decimal places as the original values. Percentages will be displayed with 1 decimal place; except percentages will not be presented when the count is zero and 100% will be presented as an integer.

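### SAP Section 7.8 counts antibody-positive samples where the endpoint and the protocol call for subjects, and its treatment-emergent and boosted percentages include subjects who cannot show the response

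*SAP*

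**What the plan says.** The endpoint in SAP Section 2.2.5 is "Incidence of ADA directed against pegcetacoplan peptide or PEG". Protocol Section 12.8.1 says that the antibody data "will be summarized by the number and percentage of subjects with confirmed positive anti-therapeutic antibodies".

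SAP Section 7.8 makes two summary commitments:

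- **Overall positivity, by sample.** "The number and percentage of samples confirmed positive for ADA response will be summarized by treatment groups". It does not say whether samples are pooled over visits or shown visit by visit, or whether the pre-dose Day 1 sample counts.
- **Response type, by subject.** "The number and percentage of subjects with treatment-emergent and treatment-boosted responses will be presented by treatment group". Treatment-emergent means "a confirmed positive antibody result postdose after a negative antibody result reported at baseline". For the other type, "Treatment-boosted response is defined as a ≥ 4 -fold increase in titer from the baseline level". No denominator is given for either.

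The general rule in SAP Section 13.1 fills that gap: "Unless stated otherwise, for all percentages, the number of subjects in the analysis population for the treatment group will be the denominator". SAP Section 7 makes the Safety set the population for safety summaries, and SAP Section 4.4 defines that set as randomized subjects with at least one injection. It sets no condition on antibody results.

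SAP Section 1 states that the SAP supersedes the protocol's analysis plan. SAP Section 15, which lists the changes from the protocol, does not mention antibodies.

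**The concern.** Incidence is a property of subjects. A sample percentage mixes how many subjects respond with when they respond, how long the response lasts and how often they were sampled. It cannot separate many brief responders from a few persistent ones. Because the SAP takes precedence, the subject count in the protocol drops out. The two subject-level summaries do not restore it: a subject who is positive at baseline and stays positive without a 4-fold rise falls in neither.

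The second issue follows from the SAP's own definitions. A subject who is positive at baseline cannot have a treatment-emergent response, and a subject without a baseline titer has nothing to boost. A subject with no post-dose result can show neither. All of them stay in the default denominator, so the percentages are not response rates among those who could respond, and nothing in the table would say so.

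**Working it through.** **Inputs from the documents**

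- Antibody draws, protocol Appendices A to D: Day 1 and Months 1, 2, 6, 12, 14, 18 and 24, plus early termination. Footnote D puts the Day 1 draw before study drug.
- About 200 subjects per analysis group (PM, PEOM, pooled sham), SAP Section 3.4.

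**Reproducing the plan's own figure.** Eight scheduled draws plus early termination make 9 time points, and 9 × 2 mL = 18 mL. Both match protocol Table 3. Section 7.8 itself states no rate to reproduce.

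**Assumptions, not in the documents.** Subject incidence 10%; treatment-emergent rate among evaluable baseline-negative subjects 10%; boosted rate among evaluable baseline-positive subjects 20%; baseline positivity *b* from 2% to 40%; share of subjects without an evaluable baseline and post-dose pair *m* from 0 to 10%.

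**1. Sample percentage, if samples are pooled.** Suppose 20 of 200 subjects turn positive after dosing, each at *k* post-dose draws, and everyone gives every scheduled sample.

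Sample percentage = 20 × *k* / (200 × number of scheduled draws)

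| Reporting | Samples | *k* = 1 | All post-dose draws positive | Subject percentage |
|---|---|---|---|---|
| Month 24 (8 draws) | 1,600 | 20/1,600 = 1.25% | 140/1,600 = 8.75% (*k* = 7) | 10% |
| Month 12 (5 draws) | 1,000 | 20/1,000 = 2% | 80/1,000 = 8% (*k* = 4) | 10% |

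The pre-dose sample is 1 of 8 (12.5%) at Month 24 and 1 of 5 (20%) at Month 12. It cannot show a treatment-induced response.

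The distortion does not always run downward. If 10 of 200 subjects have antibody at every draw, the sample percentage is 80/1,600 = 5% with the Day 1 sample and 70/1,400 = 5% without it. If those 10 are positive on Day 1 only, it is 10/1,600 = 0.6% with that sample and 0% without.

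**2. Default denominator.**

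Treatment-emergent shown = 10% × (1 − *b*) × (1 − *m*)

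Boosted shown = 20% × *b* × (1 − *m*)

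| *b* | *m* | Treatment-emergent shown (10% among evaluable) | Boosted shown (20% among evaluable) |
|---|---|---|---|
| 2% | 0 | 9.8% | 0.40% |
| 2% | 10% | 8.8% | 0.36% |
| 5% | 0 | 9.5% | 1.0% |
| 20% | 0 | 8.0% | 4.0% |
| 40% | 0 | 6.0% | 8.0% |
| 40% | 10% | 5.4% | 7.2% |

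**3. Practice elsewhere in the SAP.** Section 7.2 takes laboratory percentages over subjects with available values. Section 7.1.1 leaves subjects with prior CNV in the relevant eye out of the exudative AMD incidence. Evaluable and at-risk denominators are therefore already used in this SAP.

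**The case against.** The case on the other side has several sound parts.

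- **Subject-level results are planned.** The treatment-emergent and boosted counts are per subject and describe a drug-induced response more directly than the protocol's single count. That stands. They still do not give the proportion of subjects who are positive.
- **The pooled reading is not written down.** With one scheduled draw per visit, a by-visit sample percentage equals the percentage of sampled subjects who are positive at that visit, and no dilution arises. That stands, so the 1.25% to 8.75% range is conditional. A by-visit table would still not give the proportion of subjects ever positive.
- **The denominator is a default.** Section 7.8 does not itself choose all treated subjects; that follows from Sections 13.1 and 7. The inference is sound, because nothing in 7.8 displaces the rule for these two percentages.
- **An all-treated percentage is a legitimate quantity.** It tells how many treated patients develop or boost antibodies. That stands, provided that it is labelled as such.
- **Randomization limits imbalance between arms.** At an assumed 20% baseline positivity, the chance difference between two arms of 200 has a standard deviation of √(2 × 0.2 × 0.8 / 200) = 4 percentage points. At a 10% treatment-emergent rate, that moves the comparison by about 10% × 4 = 0.4 points. Bias in the treatment-emergent comparison between arms is thus a minor matter.

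A reader might infer that every immunogenicity rate in the plan is diluted, or that the safety endpoint is necessarily understated. The documents do not support this. Pre-existing antibody can raise the sample percentage, unequal numbers of samples per subject can push it either way, and a by-visit display need not dilute at all.

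**Conclusion.** The point holds as one of unit and denominator. The overall summary uses samples where the endpoint and the protocol use subjects, the change is not recorded in SAP Section 15, and it is too substantive to pass as an editorial change. The proportion of antibody-positive subjects is not planned anywhere. The treatment-emergent and boosted percentages include subjects who, by the SAP's own definitions, cannot respond.

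The size cannot be fixed from the documents, which give no antibody rates and no baseline positivity. The sample illustration also needs pooling over visits, equal sampling and no antibody before treatment. For treatment-emergent response the effect is small when baseline positivity is low: 10% reads as 9.5% at *b* = 5% with complete sampling. For boosted response it is large throughout the assumed range: 20% reads as 0.36% to 8.0%.

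These are descriptive safety summaries. No hypothesis test or efficacy conclusion depends on them, so this is a minor but worthwhile correction.

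**What to change.** In SAP Section 7.8, report the following separately for anti-peptide and anti-PEG antibodies (the section now promises that separation only for listings), with each denominator shown:

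- (a) subjects with at least one confirmed positive post-dose sample, over subjects with at least one post-dose result;
- (b) treatment-emergent response, over baseline-negative subjects with a post-dose result;
- (c) boosted response, over baseline-positive subjects with a post-dose result.

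An all-treated percentage may be kept if labelled as such. Sample counts may stay as a supplementary display, stating whether they are pooled or by visit and whether Day 1 is included. List any remaining departure from protocol Section 12.8.1 in SAP Section 15.

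The cost is SAP wording and the denominators of one table, with no new data. The downside is that the denominator for (c) may be small and its percentage unstable, so the counts should be read with it.

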7.9. Death

Subject deaths and primary cause of death will be summarized.

7.10. Other Safety Data

Urine pregnancy test will be provided in a listing.

8. PHARMACOKINETICS ANALYSIS

All summaries and analyses of the pharmacokinetic data will be based on the Pharmacokinetic set.

Pegcetacoplan concentrations reported as BLQ will be taken as zero for linear plots, and equal to the lower limit of quantification (LLOQ) for semi-logarithmic plots. For the computation of descriptive statistics, BLQ will be taken as zero, except for the calculation of the geometric mean where the LLOQ will be used.

Pegcetacoplan concentrations will be summarized by pegcetacoplan treatment group (i.e., PM and PEOM) at each scheduled time point using descriptive statistics ((including at least Mean, SD, CV, Median, Min, Max, Geometric Mean/%CV).

Linear and log-linear individual concentration profile plots against time will be produced for each pegcetacoplan treatment group. The actual sampling time will be used on the x-axis.

Linear and log-linear median (\pm standard error) concentration profile plots against time will be produced by treatment group. The nominal sampling time will be used on the x-axis.

Linear and log-linear mean (\pm standard error) concentration profile plots against time will be produced for each pegcetacoplan treatment group (i.e., PM and PEOM), with nominal sampling time on the x-axis.

The number of subjects with values BLQ will be tabulated.

A listing of serum concentration data will be presented by treatment arm. The actual time, deviation and percent deviation from nominal time will also be listed.

The C_{\max} values are obtained from serum samples collected at Day 7 following pegcetacoplan treatment ($C_{\text{Day 7}}$) and will be listed and summarized as part of the concentration data. The results will be listed and summarized using descriptive statistics. No additional presentations are required for other pharmacokinetic parameters.

Population pharmacokinetic and exposure-response modelling of the safety and efficacy data may be performed using a separate Population Pharmacokinetic/Pharmacodynamic Analysis Plan.

9. PHARMACODYNAMIC ANALYSES

The PD parameters (CH50, AH50, and C3) will be evaluated based on the Pharmacodynamic set. Absolute values, changes from baseline and percentage changes from baseline for the PD parameters will be summarized by treatment group at each protocol specified time point using descriptive statistics.

For each PD parameter, the individual absolute values and individual changes from baseline will be presented graphically for each treatment group. Actual sampling times will be used for the graphical presentation of individual data. If a baseline PD value is zero, then the percentage change from baseline will not be calculated. For the PD plots, a BLQ value will be set equal to LLOQ.

The mean absolute values, mean changes from baseline and mean percentage changes from baseline will also be presented graphically by treatment group. Nominal sampling times will be used for the mean plots.

Individual PD parameters will be listed together with changes from baseline and percentage changes from baseline by treatment group.

10. OTHER ANALYSES

No other analyses are planned for this study.

11. INTERIM ANALYSIS

No formal interim analyses are planned for this study.

To support regulatory submissions, data cuts of the Month 12 – Month 24 data of the study may be taken prior to the final database lock and summarized prior to the final study reporting. The analysis of this data will not be used to modify the pre-planned analyses of this study.

12. DATA MONITORING COMMITTEE

An external, independent DMC reviews unmasked data across the conduct of the study approximately every 6 months. A charter for the DMC as well as a DMC statistical analysis plan was prepared separately.

13. DATA HANDLING CONVENTIONS

13.1. General Data Reporting Conventions

Continuous variables will be summarized using the number of non-missing observations (n), mean, SD, median, quartile 1, quartile 3, minimum, and maximum. Geometric mean and CV will be included for PK parameters, where appropriate. Categorical variables will be summarized using frequencies and percentages. Unless stated otherwise, for all percentages, the number of subjects in the analysis population for the treatment group will be the denominator.

Unless otherwise specified, the estimated mean and median for a set of values should be printed out to 1 more decimal place than the original values, and standard deviations should be printed out to 2 more decimal places than the original values. The minimum and maximum should report the same number of decimal places as the original values. Percentages will be displayed with 1 decimal place; except percentages will not be presented when the count is zero and 100% will be presented as an integer.

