### **9.14. Ocular Imaging**

The following ocular images will be obtained and sent to the reading center as outlined in the visit schedule. A reading center manual along with training materials will be provided to all sites which will provide information on standardized procedures for the collection, storage, and

transmission of all images. Prior to any images being taken at the site, site personnel must be properly trained and certified and test images and systems and software must be certified and validated by the reading center. Only trained and certified site staff delegated the responsibility of image collection should perform this task. Ocular images obtained as part of this study are:

- digital color fundus photographs
- FA
- SD-OCT imaging
- FAF (Heidelberg Spectralis instrument)
- NIR
- Endothelial cell count (specular microscopy): select sites only
- OCT-A: select sites only

If a patient misses a visit during which ocular images should have been taken, the images should be collected at the next scheduled study visit.

In the event that a subject is suspected to have new active CNV in the study eye and/or the fellow eye, an SD-OCT and FFA using the protocol specified procedures should be performed and sent to the reading center to confirm the diagnosis ([Section 7.5.1](#)). In addition, in select sites, OCT-A should also be captured according to the study imaging protocol and sent to the reading center.

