- F. Beginning at Day 1, perform the urine pregnancy test for women of childbearing potential at each treatment visit. If positive, perform a serum pregnancy test. If serum test is positive, study drug should not be administered and an early term visit should be completed.
- G. Only subjects that sign the separate consent for the clinical repository and genotyping will have these samples collected. A 14-mL whole-blood sample will be collected at each of the specified visits.
- H. Blood pressure, respiratory rate, heart rate, and temperature. On dosing days, vital signs should be taken predose.
- I. Height and weight should be collected at screening.
- J. Perform assessments prior to dilating the eyes.
- K. In select countries, the MNREAD or Radner Reading Charts should be done during the study visit, prior to dilating the eyes. It should be performed monocularly first, then binocularly.
- L. To be administered by the masked site staff prior to any other assessments performed on that day. In-clinic assessments on the digital application should be completed after completion of all functional tests and quality of life measures prior to dilating the eyes.
- M. At select sites, and for those subjects who decide to participate, the digital applications will be completed on an electronic device and will consist of assessments for visual function and reading speed. Subjects will receive training at Day 1 on the use of the digital applications and the electronic device and will perform the tests using the application in the clinic at Month 1, Month 2, Month 3, Month 6, Month 12, Month 18, and Month 24. Beginning at Day 1, subjects will complete the functional assessments weekly at home. Subjects should be instructed to complete the assessments on the same day each week and at approximately the same time of day each week, if possible.

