2.2.2. Key Secondary Endpoints

The key secondary endpoints include:

- Change from baseline in uncorrected monocular maximum reading speed (study eye), at Month 24 as assessed by MNRead or Radner reading charts (in select countries).
- Change from baseline in mean FRI Index score (subject-level assessment) at Month 24
- Change from baseline in NL-BCVA score (study eye) at Month 24 as assessed by Early Treatment Diabetic Retinopathy Study (ETDRS) chart.

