6.3. Analyses of Key Secondary Efficacy Endpoints

The key secondary efficacy endpoints are listed in Section 2.2.2. At the Month 12 reporting, all key secondary efficacy endpoints will be evaluated based on data from baseline to Month 12 (see Section 3.5). For the Month 12 analyses, post-baseline visits, up to and including Month 12, will be included and nominal p-values will be presented. At the time of the final study analysis, all key secondary efficacy endpoints will be evaluated based on data from baseline to Month 24, and formal statistical testing for key secondary endpoints will be performed as described in Section 6.3.1. Unless otherwise specified, all secondary efficacy endpoints will be analyzed for the mITT set.

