6.3.2. Main Analyses of Key Secondary Efficacy Endpoints

6.3.2.1. Monocular Maximum Reading Speed

Maximum reading speed will be calculated per MNRead or Radner user manuals, with no adjustment for reading inaccuracy. An additional step to cap resulting reading speed values at a maximum of 300 words per minute will be implemented. Values above 300 words per minute exceed values reported in the literature for adults with no vision impairment for MNRead (Calabrese et al. 2016) or Radner (Radner et al. 2002; Radner and Diendorfer 2014) assessments. Maximum reading speed will be calculated as the mean of the three highest nonzero reading speeds (or two, or one value, as available) (Baskaran et al. 2019; Patel et al. 2011), except when all words per minute are calculated as 0: then the maximum reading speed will be calculated as 0.

Monocular maximum reading speed in the study eye will be summarized and analyzed in a similar fashion as the primary efficacy endpoint using MMRM described in Section 6.2.2. The model will include treatment (PM, PEOM, Sham), presence of CNV in the fellow eye (yes or no), and baseline GA lesion area ($< 7.5 \text{ mm}^2$ or $\geq 7.5 \text{ mm}^2$) as fixed effects; baseline monocular maximum reading speed as well as the chart type (MNRead or Radner) as covariates, time (in months) as a factor; the time \times treatment interaction term as well as the baseline monocular maximum reading speed \times time interaction term.

The observed values for the monocular maximum reading speed will be summarized by treatment group and visit for both the study and the fellow eye. Summaries will present the descriptive statistics for baseline, absolute values and change from baseline data.

The mean change from baseline in the monocular maximum reading speed of the study eye \pm the standard error as well as the LS mean of the change from baseline in the monocular maximum reading speed of the study eye \pm the standard error will be plotted over time by treatment group.

In addition, the categorical changes (improvements of ≥ 20 to <40 , ≥ 40 to <60 , ≥ 60 and minimal/no change (-20 to 20), worsening of ≥ 20 to <40 , ≥ 40 to <60 , ≥ 60) for the study eye will be summarized by treatment group and visit.

The shift from baseline in the monocular maximum reading speed for the study eye categories over time will be presented by treatment group for the following categories:

- < 40 wpm
- 40 to < 80 wpm
- 80 to <160 wpm
- ≥ 160 wpm

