7. SAFETY ANALYSES

Safety analyses will be performed using the Safety set. Safety variables include adverse events (AEs), deaths, clinical laboratory results, vital signs, incidence of ADA against pegcetacoplan, ocular assessments (e.g., NL-BCVA, IOP and ophthalmic examinations), and ocular imaging.

At the time of the Month 12 reporting, safety summaries will be produced based on the complete Month 12 data. At the time of the final study reporting, safety summaries will be produced based on cumulative data.

For each safety variable, the last value collected before the first dose of investigational product will be used as baseline for all analyses of that safety variable. Last Observed Value (LOV) will be defined as the last valid assessment obtained after baseline. The LOV will be presented for the Month 12 reporting as well as the final study reporting.

All safety analyses will be conducted according to the actual treatment the subject received. Unless otherwise specified, all safety summaries will be performed on the Safety set.

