7.7. Other Ophthalmology Imaging Assessments

Unless otherwise stated, ocular imaging data collected will be listed by treatment group and overall for the Safety set. The summary will be performed separately by study eye and by fellow eye. The ophthalmology imaging assessments performed in this study include the following:

- Digital Color Fundus Photographs (DCFP)
 - Shift from baseline in the presence/absence of hemorrhage at each visit
- FA
 - The following analyses will be performed in all study eyes and in non-study eyes without a history of CNV at baseline (in medical history) in the corresponding eye.
 - Incidence of new CNV. This will be summarized as the cumulative number of CNV events by each visit and the cumulative incidence by that visit based on Kaplan Meier methods.
 - Incidence of new CNV by type (classic, occult, classic & occult, disciform scar) at first emergence will be summarized at each visit for the cumulative number of events.
 - Total CNV size (diameter) at first emergence will be summarized at each visit for the cumulative number of events.
- SD-OCT
 - Descriptive statistics on central subfield thickness at each visit
 - Plot of the mean change from baseline in central subfield thickness in the study eye \pm the standard error over time by treatment group.
 - Descriptive statistics on central (center point) retinal thickness at each visit
 - Shift from baseline in the presence/absence of subretinal fluid at each visit
 - Shift from baseline in the presence/absence of cystoid spaces at each visit
- Specular Microscopy

- Endothelial Cell Count is assessed using specular microscopy, and the change from baseline in cell density (cells/mm²) as well as the change from baseline in average cell-size will be summarized with descriptive statistics.
- OCT-A
 - Incidence of subclinical CNV (referred to as MNV in the datasets) determined by OCT-A in eyes without previous CNV reported in the medical history or as an adverse event in the corresponding eye at each visit.

In addition, the following summary of suspected and reading-center confirmed CNV cases will be presented by treatment group. This will be presented separately for the study eye only.

- The number and percentage of subjects with an Exudative AMD TEAE on or before Month 12 (or Month 24 if the final analysis)

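### SAP 13.1 divides the reading-speed and VFQ-25 distance and near-activity category percentages by the whole arm, although these measures are collected only in select countries; the OCT-A incidence leaves the same question open

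*SAP*

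**What the plan says.** SAP 13.1 reports categorical variables as frequencies and percentages and sets one default: "Unless stated otherwise, for all percentages, the number of subjects in the analysis population for the treatment group will be the denominator".

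The analysis populations are broad. For safety, SAP 7 says "Unless otherwise specified, all safety summaries will be performed on the Safety set". For the key secondary endpoints, SAP 6.3 says "Unless otherwise specified, all secondary efficacy endpoints will be analyzed for the mITT set", and 6.4 and 6.6 also name the mITT set. Neither set, as defined in SAP 4.3 and 4.4, depends on whether a site or country performs a particular test.

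Some measures are taken in only part of the trial:
- Reading charts. SAP 2.2.2 defines the endpoint "at Month 24 as assessed by MNRead or Radner reading charts (in select countries"), and footnote K of Protocol Appendix A reads "In select countries, the MNREAD or Radner Reading Charts should be done during the study visit, prior to dilating the eyes".
- VFQ-25 near and distance subscales. Protocol 9.9.1 marks both as select-country; SAP 2.2.3 marks the distance score as select-site.
- OCT-A. Protocol 9.14 lists "OCT-A: select sites only".

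Category summaries are planned for them by arm and visit. SAP 6.3.2.1 has bands of improvement, a middle band and bands of worsening ("minimal/no change (-20 to 20), worsening of" 20 words per minute upward), plus a shift table. SAP 6.6.2 repeats these for binocular reading, and 6.4.4 and 6.6.1 do the like for the VFQ scores. None names a denominator. The OCT-A line of SAP 7.7 plans "Incidence of subclinical CNV (referred to as MNV in the datasets) determined by OCT-A in eyes without previous CNV reported in the medical history". Eyes whose CNV was recorded as an adverse event are left out too.

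Elsewhere the SAP does depart from its default: the potentially clinically significant laboratory and vital-sign percentages (7.2, 7.3) are taken over subjects with available values.

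**The concern.** A subject in a country without the reading test stays in the denominator but can never enter any row of the table. The default is a positive rule, not a gap that a programmer would fill by habit. The explicit exceptions for laboratory and vital-sign data suggest that silence elsewhere means the default. One measure would also be reported on two bases: SAP 13.1 gives continuous summaries their non-missing n, so mean reading speed would rest on tested subjects while the reading-speed percentages would rest on the whole arm.

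The reading-speed categories describe the first key secondary endpoint to clinical readers. Subclinical CNV is listed as a safety endpoint in SAP 2.2.5, and in Phase 2 new active study-eye exudation occurred in 25 of 165 treated subjects against 1 of 81 on sham (Protocol 4.1.4). An incidence lowered by eyes that were never imaged would be unhelpful there.

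**Working it through.** The documents state no tested fraction and no expected rate for these summaries, so there is no planned figure to reproduce.

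**Inputs**
- Arm size N: 600 × 2/6 = 200 for each pegcetacoplan arm and 100 + 100 = 200 for pooled sham (SAP 3.4). The mITT set may be somewhat smaller.
- Tested fraction f = n tested / N: not in the documents, assumed below.
- True proportion p among those tested: assumed below.

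**1. Multi-category tables.** Reported percentage = (p × n tested) / N = p × f. Suppose 30% of tested subjects worsen by 20 words per minute or more.
- f = 0.70: 140 tested, 0.30 × 140 = 42 worsen, and 42/200 = 21%. The other rows together hold 98/200 = 49%. The column sums to 70%; the 60 untested subjects (30%) are in no row.
- f = 0.90: 0.30 × 0.90 = 27%, and the column sums to 90%.

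**2. Difference from sham, equal f in both arms.** Reported difference = f × true difference; the ratio is unchanged. With an assumed 10% against 5%:

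| f | Active | Sham | Difference (points) | Ratio |
|---|---|---|---|---|
| 0.25 | 2.5% | 1.25% | 1.25 | 2.0 |
| 0.50 | 5.0% | 2.5% | 2.5 | 2.0 |
| 0.75 | 7.5% | 3.75% | 3.75 | 2.0 |
| 0.90 | 9.0% | 4.5% | 4.5 | 2.0 |
| Assessed subjects as denominator | 10% | 5% | 5 | 2.0 |

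**3. Unequal f.** Reported ratio = true ratio × f(active)/f(sham). A true 2.0 reads 2.0 × 0.50/0.40 = 2.5, or 2.0 × 0.25/0.30 = 1.67. Randomisation is stratified by lesion area and fellow-eye CNV only (SAP 3.2), so equal f is not guaranteed. At f near 0.5 with 200 per arm, the standard deviation of the chance difference in f is √(0.5 × 0.5 × (1/200 + 1/200)) = 0.05. A 5-point gap is therefore ordinary (2.0 × 0.50/0.45 = 2.22), while a 10-point gap is about two standard deviations.

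**4. OCT-A.** The line in SAP 7.7 supplies an at-risk restriction (no previous CNV), so the base is not every subject in the arm. Two readings remain. If the base is at-risk eyes that had an OCT-A, the incidence is p. If it is all at-risk eyes, the incidence is p × f, with f the imaged share of at-risk eyes, and the dilution in step 2 applies. The text does not choose between them.

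**The case against.** The strongest reply is that little rests on these percentages. The key secondary reading endpoint is a mean change tested by MMRM; the categories are descriptive, and SAP 6.5 rules out hypothesis testing of non-key secondary endpoints such as the VFQ-25 distance score. The drug's CNV signal is examined mainly through exudative-AMD adverse events with rates per 100 subject-years and Kaplan-Meier (7.1.1), and through fluorescein angiography and reading-centre confirmation (7.7), none of which depends on OCT-A sites. The number tested will appear in the continuous summaries of the same measures, so a careful reader can recover the rate. Coverage of the reading charts may be nearly complete: Protocol Appendix G leaves the choice of test by country and language to a manual. All of this stands, and it limits the consequence. It does not make the default right for these tables, and OCT-A has no continuous summary in 7.7 from which to recover the number imaged.

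A reader might go further and infer that untested subjects are counted as event-free. The documents do not support that for the reading and VFQ tables: an untested subject falls in no row, so the no-change row is lowered too and the shortfall from 100% is visible. Nor is every rate affected. The VFQ-25 composite is not marked as select-country, and the driving-worsening summary has its own base of subjects driving at baseline.

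The COVID minimum schedule could lower f for these tests, but at Months 6 and 18; they stay scheduled at Months 12 and 24.

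**Conclusion.** The point holds as a flaw in a stated reporting rule. Followed literally, SAP 13.1 multiplies every reading-speed and VFQ-25 distance and near-activity category percentage by f, and shrinks absolute differences from sham by the same factor. The ratio to sham survives only if f is equal across arms. The shortfall is 10% or more in relative terms whenever f is 0.90 or less, but the actual size cannot be given because f appears nowhere in the documents; every worked rate above is an assumption.

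For OCT-A subclinical CNV the finding is an ambiguity. It would be too strong to say that the plan divides by all subjects in the arm or that this incidence will be understated. No primary or key secondary inference changes, and the main CNV safety analyses stand.

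The same default also lowers by-visit categories for measures taken at all sites, such as NL-BCVA (6.3.2.3, 7.6) and FRI level (6.3.2.2), whenever visits are missed. The correction should not stop at the select-country measures.

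**What to change.** - **SAP 13.1:** state that by-visit categorical-change and shift percentages use subjects or eyes in the analysis set with a baseline and a non-missing value at that visit. Name 6.3.2.1, 6.4.4, 6.6.1 and 6.6.2, and by the same logic the NL-BCVA and FRI categories.
- **SAP 7.7, OCT-A line:** state that the incidence uses at-risk eyes (no previous CNV) with an OCT-A assessment at that visit, or with at least one post-baseline OCT-A if it is meant to be cumulative. Do not add a baseline OCT-A requirement; the present definition has none, and adding one would change the endpoint and not only its denominator.
- **Table shells:** print the number assessed beside each percentage.

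The cost is a sentence or two in the SAP and edits to the shells. The downside is smaller displayed denominators, which vary by visit.
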